**9 HUMAN SUBJECTS PROTECTIONS**

Confidentiality, individual choice and volunteerism are standard values of the UOB staff relative to their studies and practice. The earliest patient education and counseling begins at the initial contact with one of the protocol nurse coordinators or investigators. After arriving at the clinic,

subjects will have a dialog about: the disorder in question and the protocol study; questions are answered; information material is provided.

As information is gathered from this trial, clinical results will be shared with patients while insuring total patient confidentiality. Clinical data will be frequently gathered and any new significant findings(s) found during the course of the research, which may affect a patient's willingness to participate further will be explained. Moreover, in all publications and presentations resulting from this trial, patients' anonymity will be protected to the maximum extent possible; although, authorized personnel from the National Cancer Institute (NCI) and Food and Drug Administration (FDA) may have access to research files in order to verify that patient rights have been safeguarded.

### **9.1 RATIONALE FOR SUBJECT SELECTION**

Males of all racial/ethnic groups are eligible for this study if they meet the eligibility criteria. Efforts will be made to extend accrual to a representative population.

### **9.2 STRATEGIES/PROCEDURES FOR RECRUITMENT**

Referrals from within the NIH will be welcomed. This protocol also will be available through the NIH clinical trials data base at website address: <http://clinicaltrials.gov/>

### **9.3 JUSTIFICATION FOR EXCLUSIONS**

Patients with altered mental status that prevents consent or answering questions will be excluded. Patients with uncorrectable coagulopathies may be at increased risk for bleeding, and will be excluded. Patients with multiple co morbid illnesses, sepsis, or multiple high-risk medical problems may be at increased risk for morbidities or mortalities, and will be excluded at the judgment of the PI ([name] or his designee). This does not change standard biopsy exclusions. If a patient is unable to hold his or her breath for more than 5 seconds, the study data acquired may be potentially confounding and inaccurate.

### **9.4 PARTICIPATION OF CHILDREN**

Only patients 18 years or older will be enrolled in this study. Prostate cancer is extremely rare in children.

### **9.5 PARTICIPATION OF SUBJECTS UNABLE TO GIVE CONSENT**

Adults unable to give consent are excluded from enrolling in the protocol. However re-consent may be necessary and there is a possibility, though unlikely, that subjects could become decisionally impaired. For this reason and because there is a prospect of direct benefit from research participation (section 9.6), all subjects will be offered the opportunity to fill in their wishes for research and care, and assign a substitute decision maker on the "NIH Advance Directive for Health Care and Medical Research Participation" form so that another person can

make decisions about their medical care in the event that they become incapacitated or cognitively impaired during the course of the study. Note: The PI or AI will contact the NIH Ability to Consent Assessment Team for evaluation. For those subjects that become incapacitated and do not have pre-determined substitute decision maker, the procedures described in MEC Policy 87-4 for appointing a surrogate decision maker for adult subjects who are (a) decisionally impaired, and (b) who do not have a legal guardian or durable power of attorney, will be followed.

## **9.6 EVALUATION OF BENEFITS AND RISKS/DISCOMFORTS**

This study may be of benefit to subjects by allowing for an early, minimally invasive treatment for low grade confined prostate cancer, as compared to the current treatment standard. It also offers an alternative to those patients who would qualify for watchful-waiting but are uncomfortable with this approach. Those patients who are involved in active surveillance must undergo yearly prostate biopsies that themselves are painful and carry with them a risk of infection and prostatitis. The risks of this study are no greater than those of taking a watchful-waiting approach to treating minimally invasive prostate cancer.

However, for those patients who opt for this protocol there is a risk that their cancer may progress, either through the multifocal nature of prostate cancer or through the inaccuracy of the focally directed process. For these patients, this risk is minimized through thorough follow up with imaging, biopsy, and close monitoring of PSA. Finally, the discomfort that subjects may experience will be minimized as much as possible, however, prostate biopsies and post ablation pain may exist and this will be treated in accordance to the standard of care.

## **9.7 RISKS/BENEFITS ANALYSIS – MONITORING OF TRIAL**

Thus, we believe that this trial may eventually lead to improvements in the safety and delivery of ablation procedures. Although no guarantee of any benefit whatsoever will be made to the patient, experience from pre-clinical trials makes us confident that there is no increased risk to the patient from using the tracked devices that differ very little from conventional needles.

Focal thermal therapy for prostate cancer offers a treatment option intermediate between active surveillance and radical therapy for small volume, low grade prostate cancer. It prevents the side effects of radical therapy and may help decrease the chances of disease progression in active surveillance.

Potential risks associated with use of the Visualase laser thermal therapy system include bleeding, infection, pain, urinary tract symptoms, and damage to the rectal wall, bladder problems, and erectile dysfunction. Visualase applicator placement will be performed under sterile conditions with appropriate anesthesia (local, spinal, or general). If a course of prophylactic antibiotics or analgesics is administered according to standard clinical practice for this type of procedure, this information should be documented as a concomitant medication.

Potential risks associated with the thermal ablation treatment include pain, thermal injury to the adjacent organs, erectile dysfunction, the inability to urinate, and blood in the urine. MR-thermometry and feedback control using the Visualase system minimize the risk of overheating critical structures or areas outside of the intended target tissue.

No serious side effects or complications have been observed in any patients treated to-date with thermal ablation using Visualase.

Minimal risks are inherent within this protocol and include the physical risks of phlebotomy, and imaging contrast.

- Risk Level: Likely but not serious:
  - Risks from a skin puncture (perineum) include some discomfort associated with percutaneous analgesia and a risk of bruising, small scar formation, and a small chance of infection.
  - Voiding irritation frequency and urgency after the procedure secondary to urinary catheter which should be self resolving within a few days if removal.
  - Urinary retention after catheter removal.
  - The safety and efficacy of gadolinium contrast has been well documented and a reaction is less likely while on protocol, due to all patients required an MRI with gadolinium to be evaluated as a possible candidate
  - Minimal risks are associated with the medical procedure of obtaining blood and include some discomfort and bruising.
- Risk Level: Unknown incidence but not serious
  - Erectile Dysfunction
  - Hematuria
- Risk Level: No known risk:
  - There are no known health hazards of ultrasound or MRI at power levels employed for diagnostic purposes
- Risk Level: Very unlikely, but serious:
  - Urinary fistula from ablation of the prostate with rectum.

The PI will continue to monitor the study along with reporting adverse events to the IRB. If there is mortality the study will be paused and a determination of cause will be pursued. If the cause was due to the laser therapy the pilot study will be concluded. Also, regarding other complications rates if the 30 day complication rate of serious events exceeds 2 patients a further analysis of the technique will be performed as well as pausing and possible concluding the study if changes cannot be made for improvement.

## **9.8 CONSENT PROCESS AND DOCUMENTATION**

The investigator will inform patients and their family members (if appropriate) of the purpose, alternatives, treatment plan, research objectives and follow-up of this trial. The investigator will then provide a copy of the IRB-approved informed consent document for this study. The patient will be allowed to take as much time as he/she wishes, in deciding whether or not to participate. The original signed consent goes to Medical Records; copy placed in research record.

Version Date: 07/13/2017

CC Protocol #: 11-C-0158

Amendment G

*Image Guided Focal Prostate*

All patients must have a signed informed consent form and an on-study (confirmation of eligibility) form filled out and signed by a participating investigator before entering on the study.

For the optional research biopsy in the in the protocol, the patient will consent at the time of the procedure. If the patient refuses the optional biopsy at that time, the refusal will be documented in the medical record and in the research record.

### **9.8.1 Telephone consent**

The informed consent document will be sent to the subject. An explanation of the study will be provided over the telephone after the subject has had the opportunity to read the consent form. The subject will sign and date the informed consent. A witness to the subject's signature will sign and date the consent.

The original informed consent document will be sent back to the consenting investigator who will sign and date the consent form with the date the consent was obtained via telephone.

A fully executed copy will be returned via mail for the subject's records.

The informed consent process will be documented on a progress note by the consenting investigator and a copy of the informed consent document and note will be kept in the subject's research record.

Version Date: 07/13/2017

CC Protocol #: 11-C-0158

Amendment G

Image Guided Focal Prostate

**10 APPENDICES**

**10.1 APPENDIX A - INTERNATIONAL PROSTATE SYMPTOM SCORE (IPSS)**

Name:

Date:

	Not at all	Less than 1 time in 5	Less than half the time	About half the time	More than half the time	Almost always	Your score
Incomplete emptying Over the past month, how often have you had a sensation of not emptying your bladder completely after you finish urinating?	0	1	2	3	4	5	
Frequency Over the past month, how often have you had to urinate again less than two hours after you finished urinating?	0	1	2	3	4	5	
Intermittency Over the past month, how often have you found you stopped and started again several times when you urinated?	0	1	2	3	4	5	
Urgency Over the last month, how difficult have you found it to postpone urination?	0	1	2	3	4	5	
Weak stream Over the past month, how often have you had a weak urinary stream?	0	1	2	3	4	5	
Straining Over the past month, how often have you had to push or strain to begin urination?	0	1	2	3	4	5	

	None	1 time	2 times	3 times	4 times	5 times or more	Your score
Nocturia Over the past month, many times did you most typically get up to urinate from the time you went to bed until the time you got up in the morning?	0	1	2	3	4	5	

Total IPSS score	
------------------	--

Quality of life due to urinary symptoms	Delighted	Pleased	Mostly satisfied	Mixed – about equally satisfied and dissatisfied	Mostly dissatisfied	Unhappy	Terrible

Version Date: 07/13/2017

CC Protocol #: 11-C-0158

Amendment G

*Image Guided Focal Prostate*

If you were to spend the rest of your life with your urinary condition the way it is now, how would you feel about that?	0	1	2	3	4	5	6
--	---	---	---	---	---	---	---

Total score: 0-7 Mildly symptomatic; 8-19 moderately symptomatic; 20-35 severely symptomatic.

## 10.2 APPENDIX B - SEXUAL HEALTH INVENTORY FOR MEN

### PATIENT INSTRUCTIONS

Sexual health is an important part of an individual's overall physical and emotional well-being. Erectile dysfunction, also known as impotence, is one type of very common medical condition affecting sexual health. Fortunately, there are many different treatment options for erectile dysfunction. This questionnaire is designed to help you and your doctor identify if you may be experiencing erectile dysfunction. If you are, you may choose to discuss treatment options with your doctor.

Each question has several possible responses. Circle the number of the response that **best describes** your own situation. Please be sure that you select one and only one response for **each question**.

### OVER THE PAST 6 MONTHS:

1. How do you rate your confidence that you could get and keep an erection?

Very low	Low	Moderate	High	Very high
1	2	3	4	5

2. When you had erections with sexual stimulation, how often were your erections hard enough for penetration (entering your partner)?

No sexual activity	Almost never or never	A few times (much less than half the time)	Sometimes (about half the time)	Most times (much more than, half the time)	Almost always or always
0	1	2	3	4	5

3. During sexual intercourse, how often were you able to maintain your erection after you had penetrated (entered) your partner?

Did not attempt intercourse	Almost never or never	A few times (much less than half the time)	Sometimes (about half the time)	Most times (much more than, half the time)	Almost always or always
0	1	2	3	4	5

4. During sexual intercourse, how difficult was it to maintain your erection to completion of intercourse?

Did not attempt intercourse	Extremely difficult	Very difficult	Difficult	Slightly difficult	Not difficult
0	1	2	3	4	5

5. When you attempted sexual intercourse, how often was it satisfactory for you?

[figure not shown]
Did not attempt intercourse	Almost never or never	A few times (much less than half the time)	Sometimes (about half the time)	Most times (much more than, half the time)	Almost always or always
0	1	2	3	4	5

**SCORE** \_\_\_\_\_

[figure not shown]
Add the numbers corresponding to questions 1-5. If your score is 21 or less, you may want to speak with your

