#### **1.1.2 Secondary Objective(s):**

- To evaluate tolerability of treatment
- To determine changes in imaging and biopsy characteristics after thermal ablation of localized prostate cancer
- To obtain preliminary data, as a follow-up to this study, regarding the effect of thermal ablation using Visualase on short and long term complication rates
- To compare Visualase estimates of thermal damage post contrast MRI images.
- Determine outcome of laser ablation for treatment of prostate cancer using serial PSA, PSA density, changes in imaging, IPSS, and SHIM.

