### **3.3 QUESTIONNAIRES**

#### **3.3.1 International Prostate Symptom (Appendix A: IPSS), and the Sexual Health Inventory for Men (Appendix B: SHIM)**

Patients with prostate cancer may be asked to complete the International Prostate Symptom (Appendix A: IPSS), and the Sexual Health Inventory for Men (Appendix B: SHIM) questionnaires. These validated tools assess issues in prostate cancer patients. Questionnaires to be administered at all office follow up visits as described in Appendix D: Study Calendar.

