3.4.2.1.2 Day 1 post operatively

3.4.2.1.3 6 months

3.4.2.1.4 12 months, and

3.4.2.1.5 24 months, and 36 months after the treatment.

3.4.2.1.6 Then yearly thereafter for evaluation under the care of the local medical physician, but data will not be collected on this study (this utilizes the Cleveland clinic post operative imaging protocol used in kidney cancer).

3.4.2.2 Clinic Visits will occur at 3, 6, and 12, 18, 24 months post procedure, then yearly thereafter for a total of 3 years, and include:

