3.4.2.2.3 Completion of IPSS, and SHIM evaluations

3.4.2.3 Prostate biopsy follow up: (Standard and MR Image guided biopsy of treated targets and any new targets) at 12, 24 months. Further biopsies at 36 months are optional and

*Image Guided Focal Prostate*

additional biopsies as clinically indicated. (Biopsies can be obtained within +/- 1 month of the target time table)

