Frequency of the outcome measures, response and toxicity will be reported. Paired Student t test will be used to compare the difference between continuous variables (PSA, MRI imaging parameters) measured at baseline and at each follow-up visit. Prior to performing the paired t-test, the distribution of the underlying data will be assessed, and adequate transformation will be undertaken to ensure that the distribution of the transformed data is approximately normal. Descriptive statistics such as frequencies and percentages of categorical variables will be reported. In addition, McNemar's test, though may not have adequate power for this pilot study, will be explored to evaluate the difference in proportion between baseline and at each follow-up.

Longitudinal profiles of parameters recorded in the questionnaires over the course of follow-up for each patient will be plotted and the associated summary statistics such as mean, standard deviation, and mean change between successive follow-up visits will be reported. In addition, linear and non-linear mixed effects models will be explored to model the longitudinal profiles of the parameters of interest. In these models, random intercept will be used to incorporate the within-patient correlation of the repeated observations. If deemed appropriate, random slope will be added to the model to allow for the slope of profile to vary between patients.

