**10.4 APPENDIX D: STUDY CALENDAR**

Procedure	Screenin g/ Baseline	Treatment		3 Mos	6 Mos	12 Mos	18 Mos	24 Mos	36 Mos
		Day 0	Day 1						
History and PE	X	X	X	X	X	X	X	X	X
Digital rectal exam	X		X	X	X	X	X	X	X
Vital signs	X	X		X	X	X	X	X	X
NIH Advanced Directives Form 	X								
Labs									
CBC	X			X	X	X	X	X	X
PT/PTT/INR	X			X	X	X	X	X	X
Chem 7	X			X	X	X	X	X	X
PSA blood level	X			X	X	X	X	X	X
CMP	X								
Urinalysis and culture	X			X	X	X	X	X	X
Prostate Biopsies (10-12 cores)	X								
Prostate biopsy F/U						X		X	X b
Thermal Therapy		X							
Metastatic disease work up: may include CT or MRI or Bone scan c	X								
MR Imaging	X	X	X		X	X		X	X
Trans rectal ultrasound	X								
Questionnaires (IPSS, SHIM)	X			X	X	X	X	X	X
Response Evaluation	X	X	X		X	X		X	X
Adverse Events		X						X	X
Concomitant Medications		X						X	X

 As indicated in section 9.5 all subjects will be offered the opportunity to complete an NIH advanced directives form. This should be done preferably at baseline but can be done at any time during the study as long as the capacity to do so is retained. The completion of the form is strongly recommended, but is not required.

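### Three patient-reported measures do not fit their use: the month-3 SHIM recalls 3 pre-treatment months, pain is unobservable under general anesthesia, and the tools labelled for incontinence ask nothing about leakage

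*Combined protocol and SAP*

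**What the plan says.** **SHIM.** The form in Appendix B asks about function "OVER THE PAST 6 MONTHS". Section 3.3.1 has "Questionnaires to be administered at all office follow up visits as described in Appendix D: Study Calendar". Section 3.4.2.2 states "Clinic Visits will occur at 3, 6, and 12, 18, 24 months post procedure", followed by a visit at 3 years, and includes "Completion of IPSS, and SHIM evaluations" at each. The calendar in Appendix D agrees: baseline, then months 3, 6, 12, 18, 24 and 36. Section 1.1.2 makes the SHIM a secondary outcome, judging the result of treatment "using serial PSA, PSA density, changes in imaging, IPSS, and SHIM". For the questionnaires, Section 8 says that "mean change between successive follow-up visits will be reported" and that "linear and non-linear mixed effects models will be explored to model the longitudinal profiles". It has no provision for the recall window.

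**Pain.** Section 8 puts pain first among the outcomes of interest during thermal treatment, but the list that further defines those outcomes does not define pain. The only operational form is Section 3.7.1.1, a patient who declines to go on because of pain although medication is available. Section 3.2.2.1 has general anesthesia induced on the MRI table before draping, and Section 3.2.2.2 keeps the patient in the scanner until therapy ends. Section 9.7, on applicator placement, allows local or spinal as well as general anesthesia.

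**Continence.** Section 2.2 presents the IPSS and SHIM as the tools for potency and incontinence. Section 6.3 grades adverse events by CTCAE 4.0 and undertakes to follow the complications in a cryosurgery table, one of which is incontinence.

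**The concern.** The Précis justifies focal ablation by the continence and potency it should spare, and tolerability is a secondary objective in Section 1.1.2. These are the readouts that bear on that case.

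A month-3 SHIM score that partly describes life before treatment can hide an early loss and then, once the window has moved past Day 0, look like deterioration between months 3 and 6. Months 3 and 6 are also the scheduled readings that fall clearly before the first follow-up biopsy at month 12. Section 7.2.3 names erectile dysfunction among the symptoms that biopsy may cause.

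If every patient is under general anesthesia, a report of no pain during treatment follows from the procedure and says nothing about tolerability. If the IPSS is read as a continence measure because of its label, a stable score could be taken as evidence on a symptom it does not ask about.

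**Working it through.** **Section 8's own figures.** None of the three points enters them.
- Stopping rule: an exact patient-by-patient binomial calculation (stop at 3 events in patients 3-5, 4 in 6-10, 5 in 11-15) gives 0.0237 at an event rate of 0.1 and 0.808 at 0.40. The plan states 0.023 and 0.81.
- 80% interval width, 2 × z(0.90) × √(p(1−p)/15): 0.1985 at p = 0.1 and 0.2647 at p = 0.2. The plan states 0.19 and 0.26.

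**SHIM**

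1. Share of the 6-month window before Day 0 at month m: max(0, 6 − m)/6. Month 3: 3/6 = 50%. Months 6, 12, 18, 24 and 36, on schedule: 0%. The IPSS symptom items look back one month, so they do not share the problem.
2. Six follow-up visits give five successive changes (3-6, 6-12, 12-18, 18-24, 24-36). One of the five uses month 3. If baseline-to-month-3 is also reported, it is two of six.
3. Illustration, assuming an immediate and lasting loss of d points. Let w be the weight the patient gives to the pre-treatment months; the documents give no value for it. Month 3 records a loss of (1 − w)d and month 6 records d, so the artificial 3-to-6 decline is d − (1 − w)d = wd.

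| w | Loss seen at month 3 | Artificial 3-to-6 decline |
|---|---|---|
| 0 | d | 0 |
| 0.25 | 0.75d | 0.25d |
| 0.5 (even recall) | 0.5d | 0.5d |
| 1 | 0 | d |

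With even recall, a true 8-point drop shows as 4 points at month 3 and a further 4-point fall by month 6.

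4. The same check for a transient loss: d points lost for 3 months, then full recovery, with even recall. Month 3 averages three untreated months and three months of loss: 0.5d. Month 6 averages three months of loss and three recovered: 0.5d. The 3-to-6 change is 0, although function recovered between the visits, and month 6 still shows a loss that has gone.

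**Pain**

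1. Sections 3.2.2.1 and 3.2.2.2 together place the whole ablation under general anesthesia. Such a patient can neither report pain nor decline to continue, so the Section 8 outcome and 3.7.1.1 have nothing to record.
2. Section 9.7 admits other anesthesia, without saying who would receive it.
3. The pain that the plan expects comes afterwards. Section 9.6 mentions pain after ablation, and Section 6.3 cites a series of 12 prostate laser patients with perineal discomfort in 25%, that is 3 of 12 (exact 95% interval 5% to 57%). If that rate carried over, 0.25 × 15 = 3.75, or about 4 patients here (interval 0.8 to 8.6). No scheduled score would describe them.

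**Continence**

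1. Items: 7 IPSS symptom + 1 IPSS quality of life + 5 SHIM = 13. Items on leakage: 0. The nearest is the IPSS urgency item, on the difficulty of postponing urination.
2. The cryosurgery table in Section 6.3 gives incontinence rates of 1.3% to 7.5%. Expected cases in 15 patients: 15 × 0.013 = 0.2 to 15 × 0.075 = 1.1. Seeing 0 of 15 leaves a one-sided 95% upper limit of 1 − 0.05^(1/15) = 18%.

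**The case against.** The best reply on the SHIM is that the overlap is certain but its effect is not. The weight w is unknown, the artificial decline needs a loss that lasts, and the first SHIM item asks about confidence in the present tense, so half of the window need not be half of the score. Only one of the five successive changes is touched. All of this stands, and it is why no single size is given. It does not remove the problem, because the plan commits to reporting that one change and says nothing about how to read it.

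A reader might go further and infer a known bias in the mixed-model slope, or fault the plan for putting baseline on one straight line with follow-up. The documents support neither. Section 8 only explores models, non-linear ones included, and fixes no linear slope. The paired t-test names only PSA and MRI parameters, so nothing here rests on it.

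On pain, a reader might infer that the outcome can never occur. Section 9.7 prevents that reading: a patient under local or spinal anesthesia could report pain. What stands is that the sections conflict. Pain after the procedure also has routes into the record: CTCAE grading, the Day 1 examination, complications and medications noted at catheter removal, and analgesics logged as concomitant medication. These record events and treatment; they are not a scheduled measure of pain.

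On continence, a reader might infer that the study does not look for incontinence at all. It does, through adverse events and the Section 6.3 data points, with urodynamic studies if voiding is abnormal (Section 3.4.2.4.6). Section 8 draws no continence conclusion from the IPSS. The fault is mainly a label.

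**Conclusion.** The point holds in three parts of unequal weight.

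- **SHIM: should be changed.** Half of the month-3 window precedes ablation. The month 3-to-6 change can understate an early potency loss and show a decline that did not happen, by anything from 0 to the full loss. The size depends on how patients weight the recalled months and on whether the loss lasts, and the documents settle neither.
- **Pain: should be changed.** Under the procedure as specified, pain during ablation and refusal because of pain cannot be observed, and the text does not say which patients, if any, would be exceptions.
- **Continence: minor.** None of 13 items asks about leakage, so the Section 2.2 label is wrong. Incontinence is otherwise captured as an adverse event.

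The SHIM and continence readouts are secondary or descriptive; pain is one of several outcomes under Section 8's primary goal. The justification for 15 patients and the stopping rule do not change.

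**What to change.** 1. **SHIM.** In Section 8, make month 6 the first post-treatment value for change from baseline and in the mixed models. Show month 3 descriptively, with a note on its recall window. This needs no new data. The small cost is less weight on the earliest reading, and the month-6 score still averages over months 0 to 6, so the report should say so.
2. **Pain.** Record the anesthesia type. Apply intraprocedural pain and Section 3.7.1.1 only to patients not under general anesthesia, and reconcile Section 9.7 with 3.2.2.1. Make the pain outcome a 0-10 score at recovery, Day 1 and catheter removal. These contacts already exist, so the cost is 3 entries per patient, 3 × 15 = 45 in all.
3. **Continence.** Either take incontinence out of the Section 2.2 label, at no cost, or add one leakage or pad question at baseline and the six questionnaire visits: 7 × 15 = 105 answers. With 0.2 to 1.1 cases expected at the cryosurgery rates, such an item supports description only.

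The three changes can be adopted separately.

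### The SHIM total mixes sexual inactivity with erectile function, and Section 8 summarises it with no split by baseline function and no count of inactivity responses

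*Combined protocol and SAP*

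**What the plan says.** SHIM is one of the measures in the last secondary objective (Section 1.1.2). It is collected at baseline and at 3, 6, 12, 18, 24 and 36 months (Appendix D).

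On the form (Appendix B), question 1, "How do you rate your confidence that you could get and keep an erection", runs from 1 to 5. Question 2 offers 0 for "No sexual activity", and questions 3 to 5 offer 0 for "Did not attempt intercourse". On all four, the poorest answer about function scores 1. The scoring line begins "Add the numbers corresponding to questions 1-5. If your score is 21 or less, you may want to speak with your", with no step that treats a 0 as not assessable.

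The analysis text in Section 8 says "Longitudinal profiles of parameters recorded in the questionnaires over the course of follow-up for each patient will be plotted". It adds the mean, SD and mean change between successive visits, and exploratory mixed models with a random intercept. It names no subset by baseline erectile function, no term for sexual activity and no rule for the zeros.

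Eligibility limits baseline IPSS (2.1.2.6) but not SHIM. Criterion 2.1.1.8 admits men with recurrent or residual tumour after earlier prostate cancer treatment.

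**The concern.** A 0 on questions 2 to 5 records that nothing was attempted, not how well erection works. Once it is summed, a man without a partner, or one who chooses not to attempt intercourse, looks like a man with severe dysfunction. At the other end, men who enter with very low totals can show almost no decline and so dilute the mean loss. Nothing in eligibility keeps such men out, and previously treated men may be among them.

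Avoiding erectile dysfunction is part of the case for focal ablation in the précis, and Section 9.7 places it under "Risk Level: Unknown incidence but not serious". A SHIM summary from about 15 men should therefore let a reader tell lost function from inactivity and from low starting values.

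**Working it through.** The documents give no SHIM effect size, SD, power or event rate, so there is no planned figure to reproduce. The inputs are the Appendix B item codes and N = 15 from Section 8. The numbers of men and the score changes below are assumptions.

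**1. Possible totals**
- Active on every item: minimum 1 + 4 × 1 = 5, maximum 5 × 5 = 25.
- Fully inactive: question 1 only, so 1 to 5.

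A total of 5 can thus be an inactive man with very high erectile confidence, or an active man with the worst answer to every question.

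**2. Shift from inactivity alone.** Hold question 1 constant. A man who was active on every item loses his whole sum on questions 2 to 5, which is between 4 × 1 = 4 and 4 × 5 = 20 points. If k men do this, the mean over 15 moves by k × fall / 15.

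| Change per man | Fall | k = 1 | k = 2 | k = 3 |
|---|---|---|---|---|
| 25 to 5 | 20 | −1.33 | −2.67 | −4.0 |
| 22 to 4 | 18 | −1.2 | −2.4 | −3.6 |
| 18 to 4 | 14 | −0.93 | −1.87 | −2.8 |

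The 20-point fall is the upper limit. A man who stays sexually active but attempts no intercourse loses at most 3 × 5 = 15 points, or 15/15 = 1.0 on the mean.

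**3. Room to fall.** A man with baseline total b can lose at most b − 1. At b = 5 that is 4 points, and for an active man at 5 these can come only from switching to 0 responses. If m of 15 men show no change and the rest each lose D points, the all-patient mean loss is (15 − m) × D / 15. With m = 5:
- D = 6 gives 10 × 6 / 15 = 4.0.
- D = 8 gives 10 × 8 / 15 = 5.33.

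Both are one third below the loss in the men who could fall.

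**4. Cancellation.** Three men fall from 22 to 10 (−36 in total), and two inactive men resume activity, from 5 to 22 (+34). The mean change is (−36 + 34)/15 = −0.13, although three men lost 12 points each.

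**5. A baseline cut at 22.** A man with even one 0 response can total at most 4 × 5 = 20. Every man at 22 or more therefore answered all items as active at baseline. The cut removes baseline inactivity by construction, but it does nothing about zeros after treatment.

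**The case against.** Several objections carry weight.

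- **Individual profiles are planned.** With 15 men, each starting level and each large fall would be visible. This stands as a partial safeguard, mainly against the dilution in step 3 and the cancellation in step 4. It does not show whether a fall in the total came from inactivity or from lost function.
- **A reader might infer that SHIM cannot fall in men already impotent.** The form does not support that. Only a total of 1 cannot fall; a man at 15 can lose 14 points and a man at 21 can lose 20. Having almost no room applies only to very low totals.
- **A reader might infer that a potency-loss rate would be understated.** Section 8 plans no proportion at SHIM 21 or less, and on the form that value is advice to the patient. The McNemar test is exploratory and not tied to SHIM.
- **The 20-point fall is an extreme.** The form looks back six months, so at the 3-month visit it still covers about three months before treatment. A previously active man who is only recovering should not answer 0 there. Later visits lack this protection.
- **A 0 after treatment can be a result of the harm.** Men who lose erections may stop attempting intercourse, so removing those totals could remove the men who were harmed. This stands and limits the remedy.
- **SHIM is secondary and descriptive, and not the only source.** CTCAE grading (Section 6.3) and the history at each follow-up visit can also record erectile dysfunction. The primary objective does not depend on SHIM.

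**Conclusion.** The point holds as a weakness in the planned summary of a secondary measure. Appendix B codes inactivity below the worst function, and Section 8 has no step that separates the two or accounts for baseline level. One man's change to full inactivity can move a 15-man mean by up to about 1.3 points, with smaller shifts for more ordinary starting scores. Dilution by low starters is in proportion to their share, one third if 5 of 15 show no change.

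That the mean covers all patients is inferred from the absence of any restriction in Section 8. The share of men affected is assumed, because the documents give no baseline SHIM or activity data. They therefore do not support saying that the summary will show false harm or will hide real harm, only that it could do either and that the planned outputs would not reveal the cause. The change is a cheap improvement and not a threat to the primary aim.

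**What to change.** In Section 8, keep the all-patient SHIM summary and the individual profiles, and add:

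1. SHIM change from baseline at each visit in men with baseline SHIM 22 or more (just above the form's own cut-off of 21), with that number as the denominator. Show the remaining men separately, since many of them still have room to fall.
2. At each visit, the number of men giving a 0 response on questions 2 to 5.
3. Question 1 for every man at every visit, since it has no inactivity code.
4. If a summary without totals that contain post-treatment zeros is wanted, label it a sensitivity analysis only, and state that men may stop attempting intercourse because of erectile dysfunction.

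The form already collects every item, so no visit, procedure or patient is added. The cost is a smaller denominator for the subgroup summary; for example, if 5 of 15 men start at 21 or less, it rests on 10 men.
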